6.1.2 Sample size calculations for serum mAb concentrations

Primary Objective 2 of this study is to evaluate serum concentrations of PGDM1400LS, VRC07-523LS and PGT121.414.LS at several timepoints (ie, pharmacokinetics) following single or multiple IV or SC administrations. This objective is descriptive in nature, and will be accomplished by estimating the mean serum concentration of each mAb within each active arm at specific timepoints following product administration. The precision with which a true mean concentration can be estimated from observed data depends on the standard

deviation (SD) of the measurements and the sample size. [Table 6-3](#) displays two-sided 95% confidence intervals for the mean drug concentration for several values of the observed average drug concentration. The construction of these confidence intervals assumed sample sizes of $n = 12$ per arm, reflecting an attrition rate of 20% compared to a planned treatment group size of 16 participants. The calculations assumed that log-transformed serum concentrations are approximately normally distributed. To account for the small sample sizes, a t -distribution was used to construct CIs. For instance, with an observed mean \log_e serum level of $\log_e(10)$ mcg/mL and assuming a standard deviation of 0.5 for their log-transformed values, a two-sided 95% confidence interval for the true mean drug concentration level is (7.3, 13.7) (in mcg/mL) with an effective sample size of 12 participants. Of note, in the HVTN104 trial of VRC01, SD smaller than 1.0 for the \log_e -transformed serum concentrations of VRC01 were repeatedly observed over time following either IV infusions or SC injections of the study product (39, 47).

Table 6-3 Two-sided 95% confidence intervals based on observing a particular average \log_e mAb concentration in participants in any of the active arms, taking 20% attrition into consideration ($n = 12$)

Observed average \log_e -concentration (\log_e mcg/mL)	SD of \log_e -concentration (\log_e mcg/mL)	95% confidence interval (mcg/mL)
		$n = 12$
$\log_e(0.5)$	0.5	(0.4, 0.7)
$\log_e(1)$		(0.7, 1.4)
$\log_e(5)$		(3.6, 6.9)
$\log_e(10)$		(7.3, 13.7)
$\log_e(50)$		(36.4, 68.7)
$\log_e(100)$		(72.8, 137.4)
$\log_e(250)$		(182.0, 343.5)
$\log_e(500)$		(363.9, 687.0)
$\log_e(1000)$		(727.8, 1373.9)
$\log_e(0.5)$	1	(0.3, 0.9)
$\log_e(1)$		(0.5, 1.9)
$\log_e(5)$		(2.6, 9.4)
$\log_e(10)$		(5.3, 18.9)
$\log_e(50)$		(26.5, 94.4)
$\log_e(100)$		(53.0, 188.8)
$\log_e(250)$		(132.4, 471.9)
$\log_e(500)$		(264.9, 943.9)
$\log_e(1000)$		(529.7, 1887.7)

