below which no events would likely be observed. Specifically, for each treatment group of size $n = 3$ in Part A, there is at least a 90% or more chance of observing at least 1 event if the true rate of such an event is 53.6% or more; and there is at least a 90% or more chance of observing no events if the true rate is 3.4% or less. For IV administration Groups 1, 2 and 4 combined $n = 9$ in Part A, there is at least a 90% or more chance of observing at least 1 event if the true rate of such an event is 22.6% or more; and there is at least a 90% or more chance of observing no events if the true rate is 1.2% or less. For SC administration Groups 3 and 5 combined $n = 6$ in Part A, there is at least a 90% or more chance of observing at least 1 event if the true rate of such an event is 31.9% or more; and there is at least a 90% or more chance of observing no events if the true rate is 1.7% or less. For all Groups 1-5 combined $n = 15$ in Part A, there is at least a 90% or more chance of observing at least 1 event if the true rate of such an event is 14.2% or more; and there is at least a 90% or more chance of observing no events if the true rate is 0.7% or less. For each group of size $n=16$ in Part B, there is 90% or more chance of observing at least 1 event if the true rate of such an event is 13.4% or more; and there is 90% or more chance of observing no events if the true rate is 0.7% or less. For IV administration Groups 6, 8 and 10 combined with $n=48$ in Part B, there is 90% or more chance of observing at least 1 event if the true rate of such an event is 4.7% or more; and there is 90% or more chance of observing no events if the true rate is 0.2% or less. For SC administration Groups 7 and 9 combined with $n=32$ in Part B, there is 90% or more chance of observing at least 1 event if the true rate of such an event is 6.9% or more; and there is 90% or more chance of observing no events if the true rate is 0.3% or less. For all Groups 6-10 combined $n = 80$ in Part B, there is at least a 90% or more chance of observing at least 1 event if the true rate of such an event is 2.8% or more; and there is at least a 90% or more chance of observing no events if the true rate is 0.1% or less. As a reference, in HVTN vaccine trials from April 2008 through March 2018, about 1.7% of participants who received placebos experienced an SAE.

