Binomial probabilities of observing 0, 1 or more, and 2 or more events among arms of size 3 and 16 are presented in Table 6-1 for a range of possible true adverse event rates. These calculations provide a more complete picture of the sensitivity of the study design to identify potential safety problems with PGDM1400LS, VRC07-52310LS and PGT121.414.LS.

Table 6-1 Probability of observing 0 events, 1 or more events, and 2 or more events, among groups of size 3, 9, 10, 15, 20, and 30 for different true event rates

Group Size	True event rate (%)	Pr(0/n ₁)	Pr(1+/n ₁)	Pr(2+/n ₁)
3	1	0.97	0.03	<0.01
	4	0.88	0.12	<0.01
	10	0.73	0.27	0.03
	20	0.51	0.49	0.1
	30	0.34	0.66	0.22
	40	0.22	0.78	0.35
9	1	0.91	0.09	<0.01
	4	0.69	0.31	0.05
	10	0.39	0.61	0.23
	20	0.13	0.87	0.56
	30	0.04	0.96	0.8
	40	0.01	0.99	0.93
15	1	0.86	0.14	<0.01
	4	0.54	0.46	0.12
	10	0.21	0.79	0.45
	20	0.04	0.96	0.83
	30	<0.01	>0.99	0.96
	40	<0.01	>0.99	>0.99
16	1	0.85	0.15	0.01
	4	0.52	0.48	0.13
	10	0.19	0.81	0.49
	20	0.03	0.97	0.86
	30	<0.01	>0.99	0.97
	40	<0.01	>0.99	>0.99
48	1	0.62	0.38	0.08
	4	0.14	0.86	0.58
	10	<0.01	>0.99	0.96
	20	<0.01	>0.99	>0.99
	30	<0.01	>0.99	>0.99
	40	<0.01	>0.99	>0.99
80	1	0.45	0.55	0.19
	4	0.04	0.96	0.83
	10	<0.01	>0.99	>0.99
	20	<0.01	>0.99	>0.99
	30	<0.01	>0.99	>0.99
	40	<0.01	>0.99	>0.99
95	1	0.38	0.62	0.25
	4	0.02	0.98	0.9
	10	<0.01	>0.99	>0.99
	20	<0.01	>0.99	>0.99
	30	<0.01	>0.99	>0.99
	40	<0.01	>0.99	>0.99

An alternative way of describing the statistical properties of the study design is in terms of the 95% confidence interval for the true rate of an adverse event based on the observed data. Table 6-2 shows the 2-sided 95% confidence intervals for the probability of an event based on a particular observed rate. Calculations are done using the score test method (56). If none of the 15 or 80 participants receiving an antibody treatment regimen in Part A or Part B experience a safety event, the 95% 2-sided upper confidence bound for the true rate of such events in the total treated population is 20.4% or 4.6%. For each individual antibody treatment arm $n = 3$ or 16 in Part A or Part B, the 2-sided upper confidence bound for this rate is 56.1% and 19.4%, respectively.

Table 6-2 Two-sided 95% confidence intervals for the probability of observing a safety event based on observing a particular rate of safety endpoints for arms of size 3, 15, 16, 80 and 95.

Observed event rate	95% Confidence interval (%)
0/3	(0.0, 56.1)
1/3	(6.2, 79.2)
2/3	(20.8, 93.8)

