6.1.3 Sample size calculations for serum neutralization activity

Primary Objective 3 of this study is to evaluate serum neutralization titers of PGDM1400LS, VRC07-523LS and PGT121.414.LS against a panel of Env-pseudotyped viruses (57) at several timepoints following IV or SC

administrations. This objective is also descriptive in nature, and will be accomplished by estimating, within each mAb treatment group, the mean area-under-the-magnitude-breadth-curve (AUC-MB) (58) of serum neutralization titers of each mAb against the panel of viruses. The precision with which a true mean AUC-MB of neutralization titers can be estimated from observed data depends on the SD of the measurements and the sample size. [Table 6-4](#) displays two-sided 95% confidence intervals for the mean AUC-MB of neutralization titer for several values of the observed average AUC-MB of ID50 or ID80 neutralization titer. The construction of these confidence intervals assumed sample sizes of $n = 12$ per group, reflecting an attrition rate of 20% compared to the planned treatment group size of 16 participants, respectively. The calculations assumed that \log_e -transformed neutralization titers are approximately normally distributed. To account for the small sample sizes, a t-distribution was used to construct CIs. For instance, with an observed mean \log_e AUC-MB titer of $\log_e(50)$ and assuming a standard deviation of 0.5 for their log-transformed values, a two-sided 95% confidence interval for the true mean drug concentration level is (36.4, 68.7) with effective sample sizes of 12 participants, respectively. Of note, based on neutralization data against a global panel of 11 pseudoviruses in six participants in HVTN104, an SD of less than 1.0 was observed in the log-transformed AUC-MB of ID50 titers at various time-points post IV infusions of VRC01 (47).

Table 6-4 Two-sided 95% confidence intervals based on observing a particular average \log_e -AUC-MB neutralization titer in participants in any of the active arms, taking 20% attrition into consideration ($n = 12$)

Observed average \log_e -AUC-MB neutralization titer	SD of \log_e -AUC-MB neutralization titer	95% confidence interval
		$n = 12$
$\log_e(5)$	0.5	(3.6, 6.9)
$\log_e(20)$		(14.6, 27.5)
$\log_e(50)$		(36.4, 68.7)
$\log_e(100)$		(72.8, 137.4)
$\log_e(250)$		(182.0, 343.5)
$\log_e(500)$		(363.9, 687.0)
$\log_e(1000)$		(727.8, 1373.9)
$\log_e(5)$	1.0	(2.6, 9.4)
$\log_e(20)$		(10.6, 37.8)
$\log_e(50)$		(26.5, 94.4)

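### Tables 6-3 and 6-4 state n = 12 precision for any active arm, but the five Part A arms have three participants each

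*Protocol*

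**What the plan says.** Protocol Section 5.1 sets Primary Objectives 2 (serum concentrations and pharmacokinetics) and 3 (serum neutralizing activity) for both parts: PGDM1400LS alone in Part A, the three-antibody regimen in Part B.

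Section 6.1.2 calls Objective 2 descriptive and says it will be met by "estimating the mean serum concentration of each mAb within each active arm at specific timepoints following product administration". It then assumes 12 evaluable participants per arm, explained as 20% attrition "compared to a planned treatment group size of 16 participants". Table 6-3 is nevertheless captioned for "mAb concentration in participants in any of the active arms, taking 20% attrition into consideration".

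Section 6.1.3 does the same for Objective 3. It again derives n = 12 from groups of 16, and Table 6-4 is captioned for "neutralization titer in participants in any of the active arms".

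Table 1-1 and Section 6.1 give three participants in each of Groups 1-5. Sixteen is the Part B group size (Groups 6-10). The SAP repeats the objectives and group sizes but gives no precision figures for either part.

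**The concern.** Five of the ten arms cannot have the precision that the captions assign to them. Three participants cannot yield 12 evaluable values, and no Part A arm has a planned size of 16.

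Because Objectives 2 and 3 are descriptive, the expected width of the arm-level intervals is the whole sample-size justification for them. Section 4.5.2 says that no human PK data exist yet for PGDM1400LS, so Part A supplies the first such data, and its arm means are the ones whose precision goes unstated. Section 6.1.1 handles the same issue differently for safety: it gives separate figures for n = 3 and for n = 16. Sections 6.1.2 and 6.1.3 have no counterpart.

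What is at stake is how the Part A arm means are read. Someone relying on the captions would expect a mean known to within a factor of about 1.4 (SD 0.5) or 1.9 (SD 1.0).

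**Working it through.** **Inputs.** Two-sided 95% t interval on the log_e scale, back-transformed; SD 0.5 or 1.0; n = 12 from a group of 16 (Section 6.1.2). Part A arm size 3 and a 20% missing-data allowance (Section 6.1).

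**Formula.** Limits = mean × exp(± t(0.975, n−1) × SD/√n).

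**Reproducing the plan.** For n = 12, t(11) = 2.201.
- SD 0.5: 2.201 × 0.5/√12 = 0.318; exp(0.318) = 1.374; 10/1.374 = 7.3 and 10 × 1.374 = 13.7. This matches Table 6-3.
- SD 1.0: the factor is 1.888, giving (5.3, 18.9). This also matches.

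**Same formula for a Part A arm.** For n = 3, t(2) = 4.303.
- SD 0.5: 4.303 × 0.5/√3 = 1.242; exp(1.242) = 3.463; interval (2.9, 34.6).
- SD 1.0: 4.303/√3 = 2.484; exp(2.484) = 11.99; interval (0.8, 120).
- The log-scale half-width is 1.242/0.318, or about 3.9 times the tabulated one.

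**One value missing.** For n = 2, t(1) = 12.706. At SD 0.5: 12.706 × 0.5/√2 = 4.492; exp(4.492) = 89.3; interval (0.11, 893). If values are missing independently at the protocol's 20%, an arm of three loses at least one value at a given timepoint with probability 1 − 0.8³ = 0.49. Independence is an assumption made here.

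| Observed mean 10 mcg/mL | SD 0.5 | SD 1.0 |
|---|---|---|
| n = 12 (stated for any active arm) | (7.3, 13.7) | (5.3, 18.9) |
| n = 3 (Groups 1-5, complete data) | (2.9, 34.6) | (0.8, 120) |
| n = 2 (one value missing) | (0.11, 893) | not shown |

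**Table 6-4.** The same factors apply. At an observed titer of 50, the stated (36.4, 68.7) at SD 0.5 becomes 50/3.463 to 50 × 3.463 = (14.4, 173.1) for n = 3.

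**Pooled SD.** Five arms of three leave 15 − 5 = 10 degrees of freedom for a common log-scale SD, so t(10) = 2.228. At SD 0.5: 2.228 × 0.5/√3 = 0.643; exp(0.643) = 1.90; interval (5.3, 19.0). This is much narrower than the single-arm interval but still wider than the n = 12 one.

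**Part B check.** Twenty percent attrition from 16 leaves 12.8; using 12 implies 25% loss. The tables are therefore slightly conservative for Groups 6-10.

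**The case against.** The strongest reply is that the body text shows what was meant. Sections 6.1.2 and 6.1.3 tie n = 12 to groups of 16, n = 12 appears in the captions and column headers, and Part A's three per group is stated openly in several places. On this view the fault is an over-broad caption that few readers would take literally, in a descriptive objective on which no sample size depends. Much of that stands: the n = 12 arithmetic is right, and the intent is recoverable. It does not supply the missing Part A figures, and the text itself sets the aim as a mean within each active arm.

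Three stronger readings are tempting, and the documents do not support them.

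- **That the safety bound for 0/3 is wrong.** Section 6.1.1 says "the 2-sided upper confidence bound for this rate is 56.1% and 19.4%, respectively" and names the score method. The score bound for 0/3 is 3.84/(3 + 3.84) = 56.1%, so the figure is correct. The exact Clopper-Pearson bound is higher, at 70.8%, but preferring it is a choice of method. Nor is there a conflict with the statement of a 90% "chance of observing at least 1 event if the true rate of such an event is 53.6% or more": that is an exact binomial detection figure and answers a different question.
- **That three-versus-three rank tests are planned and cannot reach p < 0.05.** Sections 6.4.5.1 and 6.4.7 describe rank tests in general terms without naming Part A pairs, and Section 6.4.4.1 makes the primary concentration analysis descriptive.
- **That escalation rests on these intervals.** Section 11.3 bases it on review of safety data by the PSRT, with the SMB in specified cases. No rule there uses Tables 6-2, 6-3 or 6-4.

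**Conclusion.** The point holds as a misstatement of scope plus an omission. The precision in Tables 6-3 and 6-4 is correct for Groups 6-10 and does not apply to Groups 1-5, for which the plan states none. With complete data, a Part A arm mean is determined to within a factor of about 3.5 at SD 0.5 and about 12 at SD 1.0, compared with the tabulated 1.4 and 1.9. With one value missing, the arm-level interval is uninformative.

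These figures assume the protocol's own formula, approximate log-normality and its two illustrative SDs. They do not show that Part A is too small for its purpose or that any group size should change.

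**What to change.** - In the text of Sections 6.1.2 and 6.1.3 and in the captions of Tables 6-3 and 6-4, limit the n = 12 intervals to Groups 6-10.
- Add n = 3 rows for Groups 1-5 to both tables, or state that arm-level precision in Part A is very limited. At a mean of 10 mcg/mL the rows would read (2.9, 34.6) for SD 0.5 and (0.8, 120) for SD 1.0, with a note on what one missing value does.
- Optionally, provide in the SAP for Part A arm intervals that use a log-scale SD pooled over the five arms, reported beside the unpooled ones and labelled as assuming a common SD. Pooling spans IV and SC routes and doses from 5 to 40 mg/kg, and the documents give no evidence on whether the SD is common across them.

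The cost is table rows and wording. The downside is that the stated Part A precision looks less favourable.

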6.1.3 Sample size calculations for serum neutralization activity

Primary Objective 3 of this study is to evaluate serum neutralization titers of PGDM1400LS, VRC07-523LS and PGT121.414.LS against a panel of Env-pseudotyped viruses (57) at several timepoints following IV or SC

administrations. This objective is also descriptive in nature, and will be accomplished by estimating, within each mAb treatment group, the mean area-under-the-magnitude-breadth-curve (AUC-MB) (58) of serum neutralization titers of each mAb against the panel of viruses. The precision with which a true mean AUC-MB of neutralization titers can be estimated from observed data depends on the SD of the measurements and the sample size. [Table 6-4](#) displays two-sided 95% confidence intervals for the mean AUC-MB of neutralization titer for several values of the observed average AUC-MB of ID50 or ID80 neutralization titer. The construction of these confidence intervals assumed sample sizes of $n = 12$ per group, reflecting an attrition rate of 20% compared to the planned treatment group size of 16 participants, respectively. The calculations assumed that \log_e -transformed neutralization titers are approximately normally distributed. To account for the small sample sizes, a t-distribution was used to construct CIs. For instance, with an observed mean \log_e AUC-MB titer of $\log_e(50)$ and assuming a standard deviation of 0.5 for their log-transformed values, a two-sided 95% confidence interval for the true mean drug concentration level is (36.4, 68.7) with effective sample sizes of 12 participants, respectively. Of note, based on neutralization data against a global panel of 11 pseudoviruses in six participants in HVTN104, an SD of less than 1.0 was observed in the log-transformed AUC-MB of ID50 titers at various time-points post IV infusions of VRC01 (47).

Table 6-4 Two-sided 95% confidence intervals based on observing a particular average \log_e -AUC-MB neutralization titer in participants in any of the active arms, taking 20% attrition into consideration ($n = 12$)

Observed average \log_e -AUC-MB neutralization titer	SD of \log_e -AUC-MB neutralization titer	95% confidence interval
		$n = 12$
$\log_e(5)$	0.5	(3.6, 6.9)
$\log_e(20)$		(14.6, 27.5)
$\log_e(50)$		(36.4, 68.7)
$\log_e(100)$		(72.8, 137.4)
$\log_e(250)$		(182.0, 343.5)
$\log_e(500)$		(363.9, 687.0)
$\log_e(1000)$		(727.8, 1373.9)
$\log_e(5)$	1.0	(2.6, 9.4)
$\log_e(20)$		(10.6, 37.8)
$\log_e(50)$		(26.5, 94.4)
$\log_e(100)$		(53.0, 188.8)
$\log_e(250)$		(132.4, 471.9)
$\log_e(500)$		(264.9, 943.9)
$\log_e(1000)$		(529.7, 1887.7)

6.2 Randomization

There will be no randomization for Group 1 as they will be enrolled first. Contingent on safety data from Group 1, Groups 2 and 3 will be randomized and

enrolled simultaneously. Contingent on safety data from Groups 2 and 3, Groups 4 and 5 will be randomized and enrolled simultaneously. Contingent on data from Part A, Groups 6, 7, 8, and 9 will be randomized in blocks to ensure balance across groups for simultaneous enrollment. There will be no randomization for Group 10. A participant's randomization assignment will be computer generated and provided to the CRS pharmacist through a web-based randomization system.

6.3 Blinding

Participants and CRS staff will be unblinded to participant treatment arm assignments. Laboratory Center staff will be unblinded to whether a sample is from Part A or Part B, but will remain blinded to treatment assignment within Part A or Part B during sample analysis.

6.4 Statistical analyses

This section describes the final study analyses, unblinded as to treatment arm assignment. All safety data from enrolled participants will be analyzed according to the initial randomization assignment regardless of how many study product administrations and how much study product they received. In the rare instance that a participant receives the wrong treatment at a specific study product administration time, the Statistical Analysis Plan (SAP) will address how to analyze the participant's safety data. Analyses of safety data are modified intent-to-treat (MITT) in that individuals who are randomized but not enrolled do not contribute data and hence are excluded. Because of the brief length of time between randomization and enrollment—typically no more than 4 working days—very few such individuals are expected. The primary analysis of mAb concentration and anti-viral functional activity data are per-protocol (PP) in that only individuals who receive the expected mAb at the expected dose level within the expected visit window contribute data. Secondary analysis will also involve the MITT cohort, and when necessary account for the actual specimen collection time, and the actual time and dose amount of each product administration.

Analyses for primary endpoints will be performed using SAS and R. Additional software may be used to perform non-compartmental PK and population PK analyses (eg, Monolix). All other descriptive and inferential statistical analyses will be performed using SAS, StatXact, or R statistical software.

No formal multiple comparison adjustments will be employed for multiple primary or secondary endpoints. However, multiplicity adjustments will be made for certain primary or secondary endpoint assays, as discussed below, when the assay endpoint is viewed as a collection of hypotheses (eg, testing multiple pseudo-viruses to determine a positive antiviral functional activity response). Unless otherwise noted, all statistical tests will be 2-sided and will be considered statistically significant if $p < 0.05$.

6.4.1 Analysis variables

The analysis variables consist of baseline participant characteristics, safety, mAb concentration, mAb functionality, and ADA for primary- and secondary-objective analyses.

6.4.2 Baseline comparability

Treatment arms will be compared for baseline participant characteristics using descriptive statistics.

6.4.3 Safety/tolerability analysis

Since enrollment is concurrent with receiving the first study product administration, all participants will have received at least 1 product administration and therefore will provide some safety data.

6.4.3.1 Solicited AEs

The number and percentage of participants experiencing each type of Solicited AE sign or symptom (see Section 11.2.2) will be tabulated by severity and treatment arm and the percentages displayed graphically by arm. For a given sign or symptom, each participant's Solicited AEs will be counted once under the maximum severity for all injection visits. In addition, to the individual types of events, the maximum severity of local pain or tenderness, induration or erythema, and of systemic symptoms will be calculated. Kruskal-Wallis tests will be used to test for differences in severity between arms.

